3.3.3 Pregnancy

The number of subjects with pregnancy in each group during the study will be counted and the final pregnancy outcomes will be described according to the following categories:

- Pregnancy outcome (in pregnancy, delivered, termination)
- Neonatal status (normal, congenital anomaly, other complications or abnormalities)
- Reason for termination of pregnancy

3.3.4 Vital signs

Vital signs include: body temperature, pulse, blood pressure (systolic, diastolic).

Observations and changes from baseline at scheduled visits will be summarized descriptively. At the same time, clinical assessment will be performed for each test result (normal < abnormal but not clinically significant < abnormal and clinically significant), and a crossover table will be presented showing the worst post-baseline results (including results at unscheduled visit) and the change of test results from baseline at each scheduled visit. In addition, vital sign findings of increased toxicity or new toxicity (Grade ≥ 1) from baseline will be summarized by visit. Refer to toxicity grading in Appendix 2.

3.4 Exploratory analysis

Considering that the current number of PPS subjects does not reach the sample size of AUEC₁₋₁₅ in the protocol for the hypothesis of superiority, and the RVNA before immunization in China clinical trial is limited by 0.5 IU/mL, the only reason for the inclusion of AUEC₁₋₁₅ analysis is that the PPS is excluded because the RVNA before immunization is ≥ 0.1 IU/mL and the RVNA before immunization is less than 0.5 IU/mL, and the exploratory analysis is performed on the subjects with the same analysis method as the RVNA on Day 8 after medication.

4 Interim Analysis

No interim analysis will be performed in this study. However, after all subjects have completed the safety and efficacy observations up to Day 99 post-dose (serology results on Days 1, 4, 8, 15, 43, 99 are available), the first analysis will be performed, and a statistical analysis report and a clinical study report will be drafted

and submitted to the NMPA for review. After all subjects have completed the safety and efficacy observations 1 year post-dose, a second analysis will be performed, and a statistical analysis report and a final clinical study report will be drafted and submitted to the NMPA as supplementary documents and submitted to the FDA US for review.

5 Modifications to Statistical Analysis Plan in the Study Protocol

“The difference in RVNA rates will also be analyzed using Wald” and “rate differences and P-values adjusted for stratification factor of study site will be calculated using the CMH method” are added in the SAP compared to the clinical study protocol (version: 2.0, 06-Dec-2020).

6 References

7 Appendices

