Based on the study hypothesis, the lower limit of the 95% confidence interval (CI) of the geometric mean concentration of RVNA (test group/control group) is > 0.8 , a final sample size of 308 subjects (231 subjects in the test group and 77 subjects in the control group) is required with a type I error of 0.025 (one-sided), a power of 90%, an estimated geometric mean concentration of RVNA (test group/control group) on Day 99 post-dose of 86.94, and a CV of 17.32%, when assigning the subjects to the test group/control group at a ratio of 3:1 and considering a dropout rate of 20%. The current 1000 subjects are sufficient to ensure a 100% power under the same hypothesis.

- 3) The test group is non-inferior to the control group in the antibody positive rate of RVNA ($RVNA \geq 0.5$ IU/mL) on Day 99 post-dose (the lower limit of 95% CI of RVNA positive rate (test group/control group) > 0.9)

Based on the study hypothesis, the lower limit of the 95% CI of the ratio of antibody positive rates (test group/control group) is > 0.9 , a final sample size of 52 subjects (39 subjects in the test group and 13 subjects in the control group) is required with a type I error of 0.025 (one-sided), a power of 90%, an estimated ratio of antibody positive rates (test group/control group) on Day 99 post-dose of 1, and a CV of 98.7%, when assigning the subjects to the test group/control group at a

ratio of 3:1 and considering a dropout rate of 20%. The current 1000 subjects are sufficient to ensure a 100% power under the same hypothesis.

4) The SYN023 plus Rabies Vaccine group is superior to the HRIG plus Rabies Vaccine group in AUEC₁₋₁₅ of RVNA GMC (the lower limit of 95% CI of AUEC₁₋₁₅ ratio of RVNA GMC (test group/control group)>1.1)

Based on the study hypothesis, the lower limit of the 95% CI of AUEC₁₋₁₅ ratio of RVNA GMC (test group/control group) is > 1.1, a final sample size of 900 subjects (675 subjects in the test group and 225 subjects in the control group) is required with a type I error of 0.025 (one-sided), a power of 90%, an estimated AUEC₁₋₁₅ ratio of RVNA GMC (test group/control group) post-dose of 147.55%, and a CV of 142%, when assigning the subjects to the test group/control group at a ratio of 3:1 and considering a dropout rate of 20%. The current 1000 subjects are sufficient to ensure a 96.9% power under the same hypothesis.

2 General Statistical Considerations

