2.2 Definitions of Analysis Sets

Safety Set (SS): includes all randomized subjects who have received at least 1 dose of study drug, used as the Safety Set of the study. Based on the SS, the subjects will be analyzed for safety by actual treatment groups; and be analyzed for demographic, baseline, and efficacy endpoints by planned groups.

Per-Protocol Set (PPS): includes all randomized subjects who have received correct study drug, have been confirmed for eligibility to inclusion/exclusion criteria*, have completed the rabies vaccination on Study Day 29 as required by the protocol, have no major protocol violations affecting the efficacy evaluation, and have received sufficient wound treatment at all exposed sites and received study drug injections.

* Inclusion/exclusion criteria to be confirmed include: Category III rabies exposure with a duration of <24 hours; RVNA <0.1 IU/mL in serum collected from blood sampling at time “0” on study day 1 (WHO, 2013). In our previous clinical study experience, about 2% to 5% of enrolled subjects may have the history of vaccination with rabies vaccine. Their RVNA response may be much quicker and higher than the naive patients. Since the RVNA is a critical efficacy endpoint, the subjects with a RVNA \geq 0.1 IU mL, which indicated the prior use of rabies vaccine, should be analyzed separately.

In addition, subjects with (not limited to) the following conditions will likely be excluded from the PPS, depending on the discussion at the blinded data review meeting prior to database lock:

- Subjects will be excluded for the conditions that may impair the protection (such as immunodeficiency) as discovered after randomization.
- Subjects will be excluded if excessive treatment delay (>24 hours) is discovered.
- Subjects will be excluded if they will receive or have received protocol prohibited treatments.
- Subjects will be excluded if all of the bite wounds are discovered to have not been properly treated or injected.

The primary analysis of the efficacy endpoints will be performed by the randomized groups of study drugs based on the PPS.

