3.2.1 Primary Efficacy Analysis

3.2.1.1 GMC of RVNA on Day 8 post-dose

3.2.1.1.1 Primary Analysis

Null hypothesis: $\text{GMC}_{\text{SYN023}}/\text{GMC}_{\text{HRIG}} \leq 1.2$.

Alternative hypothesis: $\text{GMC}_{\text{SYN023}}/\text{GMC}_{\text{HRIG}} > 1.2$.

$\text{GMC}_{\text{SYN023}}$ represents the geometric mean concentration of RVNA on Day 8 post-dose in the test group and GMC_{HRIG} represents the geometric mean concentration of RVNA on Day 8 post-dose in the control group with a type I error of 0.025 (one-sided).

RVNA concentrations on Day 8 will be summarized for each treatment group with median, minimum, maximum, geometric mean, 95% CI of geometric mean,

and geometric coefficient of variation. The RVNA concentration at each scheduled visit for each subject is the geometric mean of the duplicate results.

In addition, with the treatment group and the study site used as fixed variables, the mean and standard error of adjusted RVNA (log-transformed) concentrations in two groups will be summarized using analysis of variance, and the ratio of RVNA geometric mean concentrations, 95% CI, and P-value in two groups will be calculated at the two-sided 0.05 level.

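### SAP 3.4 appears to pool subjects with Day 1 RVNA of 0.1 to <0.5 IU/mL into AUEC1-15 without a baseline RVNA term or a separate display, although SAP 2.2 asks for separate analysis

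*SAP*

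**What the plan says.** SAP 2.2 requires Day 1 RVNA below 0.1 IU/mL for the PPS. It takes a value at or above 0.1 IU/mL as a sign of earlier rabies vaccination, in words "which indicated the prior use of rabies vaccine, should be analyzed separately". Of previously vaccinated subjects it says: "Their RVNA response may be much quicker and higher than the naive patients". It puts the share of enrolled subjects with a vaccination history at about 2% to 5%.

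SAP 3.4 gives two reasons for a further AUEC1-15 analysis. The PPS has not reached the sample size planned for that endpoint, and in China the pre-immunisation RVNA limit is 0.5 IU/mL. It then refers to subjects whose only ground for exclusion from the PPS was a value of 0.1 to <0.5 IU/mL, and says that "the exploratory analysis is performed on the subjects with the same analysis method as the RVNA on Day 8 after medication". That method (SAP 3.2.1.1.1) is an analysis of variance on log RVNA "with the treatment group and the study site used as fixed variables". It has no baseline RVNA term.

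SAP 3.2.1.1.2 plans a subgroup split by Day 1 RVNA (<0.1 versus ≥0.1 IU/mL), restricted to the SS. SAP 3.2.2.1 carries it to the other GMC time points and SAP 3.2.2.3 to AUEC1-15. SAP 3.1.3 already lists the same two categories as a baseline characteristic.

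**The concern.** The same biomarker is handled in two ways. SAP 2.2 separates subjects at or above 0.1 IU/mL because their response is expected to differ. SAP 3.4 appears to merge part of that group with naive subjects in a model that cannot distinguish them.

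If these subjects (called primed below) have a much higher AUEC1-15 in both arms, merging them adds between-group spread to the residual variance. If their own vaccine response masks the difference in passive antibody, the pooled treatment ratio also moves towards 1. The second effect is plausible from the protocol's own data. In the Chinese bridging study (protocol 6.3.4), RVNA peaked at 4.55 IU/mL on Day 7 with SYN023 alone, but at 53.27 IU/mL on Day 14 with vaccine added. Days 8 to 15 make up 7 of the 14 days in the AUEC.

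An analysis introduced because of a sample-size shortfall could then be less powerful than the smaller PPS. Without results by stratum, a pooled ratio would also be hard to interpret in reports that go to two regulators.

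**Working it through.** **Inputs from SAP 1.3.3.** The superiority criterion is that "the lower limit of the 95% CI of AUEC₁₋₁₅ ratio of RVNA GMC (test group/control group) is > 1.1". The ratio and variability are "post-dose of 147.55%, and a CV of 142" percent, alpha is 0.025 one-sided, allocation is 3:1 and dropout is 20%.

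- Log-scale SD = √ln(1 + 1.42²) = 1.0507.
- Log distance to the margin = ln(1.4755/1.1) = 0.2937.

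**The plan's own figures reproduce.**

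- Control n = 1.0507² × (1 + 1/3) × (1.960 + 1.282)² / 0.2937² ≈ 179.3, rounded up to 180.
- Total evaluable = 180 × 4 = 720, and 720/0.8 = 900. This matches "a final sample size of 900 subjects (675 subjects in the test group and 225 subjects in the control group").
- Power = Φ[0.2937/(1.0507 × √(1/n₁ + 1/n₀)) − 1.96]. With 1000 evaluable it is 96.9%, as stated. With 800 it is 92.8%, with 720 it is 90.1% and with 650 it is 87.0%.

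**Assumptions.** The documents do not give the PPS count, the number added, the fold-difference in AUEC or the treatment ratio in primed subjects.

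- PPS N = 650 (range 600 to 719, that is, below the 720 required).
- Added m = 35 (range 20 to 50, which is 2% to 5% of 1000). SAP 3.4 leaves out anyone at or above 0.5 IU/mL, so the true number may be smaller.
- F = fold-higher AUEC in primed subjects, the same in both arms (1 to 10).
- r₂ = treatment ratio in primed subjects (1.4755 or 1.0).
- The 142% CV is taken to apply within each stratum.

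**Pooling formulas.** With p = m/(N + m) = 35/685 = 0.0511:

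- Pooled SD = √(1.0507² + p(1 − p)(ln F)²). This gives 1.078 at F = 3 and 1.109 at F = 5.
- Pooled distance = (1 − p) ln 1.4755 + p ln r₂ − ln 1.1. This stays at 0.2937 if r₂ = 1.4755 and falls to 0.2738 if r₂ = 1.0.
- A baseline-stratum term returns the SD to 1.0507 but leaves the distance as it is.

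| Primed subjects | No baseline term | With baseline term |
|---|---|---|
| F = 1, ratio unchanged | 88.6% | 88.6% |
| F = 3, ratio unchanged | 87.0% | 88.6% |
| F = 5, ratio unchanged | 85.1% | 88.6% |
| F = 1, ratio 1.0 | 84.0% | 84.0% |
| F = 3, ratio 1.0 | 82.1% | 84.0% |

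The comparator is 87.0% for the PPS alone.

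**Break-even.** With an unchanged ratio, setting pooled and PPS-only power equal gives ln F = SD × (N + m)/N = 1.0507 × 685/650 = 1.107, so F = 3.03. Over the assumed ranges of N and m it runs from 2.94 to 3.12. With F = 1, break-even is at a primed ratio of about 1.27; with F = 2 it is about 1.35.

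**Range.** Across N = 600 to 719 and m = 20 to 50, the most that pooling gains is 0.7 to 2.8 points (F = 1, ratio unchanged). The worst scenario examined (N = 600, m = 50, F = 10, ratio 1.0) gives 66.8% against 84.2%, a loss of 17.4 points.

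**Simulation check** (6000 runs per scenario, 650 + 35). The PPS alone gives 87.6%. F = 3 with unchanged ratio gives 87.1%. F = 5 with unchanged ratio gives 85.9% without the term and 88.0% with it. F = 3 with ratio 1.0 gives 83.2% without the term and 83.9% with it. The formula is approximate when the ratios differ, but the pattern is the same.

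**The case against.** The strongest reply is that nothing confirmatory depends on this. SAP 3.4 is labelled exploratory and lies outside the testing sequence in SAP 2.4. The confirmatory AUEC1-15 test uses the PPS, which excludes everyone at or above 0.1 IU/mL. Day 1 RVNA is measured before dosing, so pooling does not confound the randomised comparison, and extra variance or a diluted ratio makes superiority harder to show, not easier. All of this stands and sets the severity.

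Second, a reader might infer that the SAP never separates primed subjects. It does: the SS results by Day 1 RVNA are planned for the GMCs and for AUEC1-15. What is missing is narrower. That split puts everyone at or above 0.1 IU/mL into one group and does not cover the 3.4 population, and the overall SS estimates carry no baseline term.

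Third, the cut-off of 0.5 IU/mL is not explained by the shortfall alone, since SAP 3.4 also cites the limit used in China. That may explain the choice of cut-off, but it does not explain why SAP 2.2's separate analysis is set aside.

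Fourth, the text of SAP 3.4 is garbled, and an analysis of the added subjects alone is not excluded. Adding them to the PPS is an inference, though it is the reading that serves the stated sample-size motive.

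Fifth, at the SAP's own 2% to 5% share the loss is small unless the fold is large or the effect is reduced. With 800 naive subjects and an unchanged ratio, power is 92.8% alone, 92.8% when pooled at 3-fold, and 91.5% to 92.2% at 5-fold. This also stands.

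**Conclusion.** The concern holds as an inconsistency of low severity. On its likely reading, SAP 3.4 pools a group that SAP 2.2 says should be analysed separately, with neither adjustment nor a separate display.

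In the 650 + 35 example, pooling moves power from 87.0% to between 88.6% and 82.1% over the tabulated scenarios. It falls below the PPS alone only if primed AUEC is more than about 3-fold higher, or if the treatment ratio in primed subjects is smaller. All of this rests on assumed values for the PPS size, the number added, the fold and the primed ratio.

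Two stronger readings are not supported. One is that pooling will lower power: below about 3-fold with an unchanged ratio, power is the same or slightly better. The other is that SAP 2.2 forbids pooling: it says should, and it excludes these subjects only from the PPS.

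A baseline term would recover the loss from added spread (85.1% back to 88.6% at 5-fold). It would not recover the loss from a diluted effect (84.0% with the term, against 87.0% for the PPS alone), so the display by stratum is also needed.

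**What to change.** 1. In SAP 3.4, state plainly that the population is the PPS plus subjects excluded solely for a Day 1 RVNA of 0.1 to <0.5 IU/mL, if that is what is meant.
2. Add Day 1 RVNA category (<0.1 versus ≥0.1 IU/mL) as a fixed factor, alongside treatment and site, in the log-scale ANOVA of SAP 3.4 and in the overall SS supportive GMC and AUEC1-15 models.
3. Show the SAP 3.4 treatment ratio and its confidence interval separately for <0.1 and 0.1 to <0.5 IU/mL, in line with SAP 2.2.

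The cost is SAP wording, one model term and one table. The baseline value is already collected and categorised, and the confirmatory PPS analysis does not change.

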Appendix 1. Adverse Event Severity Grading Criteria

Symptoms/Signs	Grade 1	Grade 2	Grade 3	Grade 4
Induration *, swelling (optional) * * #				
> 14 years	2.5 ~ < 5 cm in longest diameter or 6.25 ~ < 25 cm ² in area	5 ~ < 10 cm in longest diameter or 25 ~ < 100 cm ² in area	≥10 cm in longest diameter or ≥100 cm ² in area	/
Rash *, redness (optional) * * #				
> 14 years	2.5 ~ < 5 cm in longest diameter or 6.25 ~ < 25 cm ² in area	5 ~ < 10 cm in longest diameter or 25 ~ < 100 cm ² in area	≥10 cm in longest diameter or ≥100 cm ² in area	/

Signs	Grade 1	Grade 2	Grade 3	Grade 4
Pyrexia * [Axillary temperature (°C)]				
> 14 years	37.3 ~ < 38.0	38.0 ~ < 38.5	38.5 ~ < 39.5	≥ 39.5

Note: Area is calculated as: $\pi \cdot A$ (longest diameter) * B (shortest diameter)/4

Appendix 2. Vital Signs Toxicity Grading

Vital Signs	Mild (Grade 1)	Moderate (Grade 2)	Severe (Grade 3)	Very severe (Grade 4)
Pyrexia	38.0-38.4°C	38.5-38.9°C	39.0-40°C	>40°C
Tachycardia (beats/min)	101-115	116-130	>130	
Bradycardia (beats/min)	50 – 54	45 – 49	< 45	
Hypertension (systolic blood pressure) - mmHg	141 – 150	151 – 155	> 155	
Hypertension (diastolic blood pressure) - mmHg	91 – 95	96 – 100	> 100	
Hypotension (systolic blood pressure) - mmHg	85 – 89	80 – 84	< 80
